2. STUDY DESIGN

Study design: Single-blind study. Patients will be randomized, at the time of implant, to HBP versus CS pacing, and remain blinded to their treatment allocation. Both treatment options use standard-of-care, FDA-approved devices. The distinction is only in the allocation toward HBP and CS pacing. Treating physicians will be aware of assignment in order to facilitate routine device follow-up. Echocardiographic and electrocardiographic evaluation will also be performed in a blinded manner.

Cross-over is permitted between treatment group allocation if:

- CS lead cannot be placed due to difficult cannulation of the CS, limited branches at the posterolateral or lateral wall, or phrenic nerve capture. These patients may then cross-over to HBP.
- HBP patients may cross-over if lead cannot be positioned with adequate stability and reasonable pacing output or if QRS width does not narrow by at least 20% or to a QRS width of \leq 130 msec.

Implant procedure will be per routine percutaneous access, as is standard for pacemaker and ICDs. All patients will receive an FDA-approved cardiac resynchronization therapy pacemaker or defibrillator device, as per standard of care outlined for the patient. In order to facilitate optimal lead placement, arterial access for levo-phase CS angiography and/or LV septal mapping to characterize site of bundle-branch block may also be performed, at the discretion of the implanting physician per his/her standard practice.

Follow-up will be performed at 2 weeks post-implant for incision check and device interrogation as is standard of care. In addition, routine device and clinical follow-up will be scheduled at 1, 3, 6, and 12 months.

Electrocardiography (i.e., ECG) will be performed pre-implant, prior to hospital discharge, at 3 months, 6 months, and 12 months. Echocardiography will be performed pre-implant, 6 months, and 12 months to evaluate for change in LVEF, chamber dimension, and wall motion with strain imaging as is standard of care in the treatment of patients with advanced heart failure. NYHA functional class and quality of life (utilizing the Kansas City Cardiomyopathy Questionnaire) will be assessed pre-implant and at 6 months.

Duration of study: 12 months

Primary endpoints: A combination of clinical, electrocardiographic, and echocardiographic endpoints will be prospectively studied. These include:

- **Clinical:** Primary clinical endpoint is a composite of heart failure hospitalization, VT/VF, and any-cause mortality at 12 months.
- **Electrocardiographic:** Change in QRS duration between pre-implant and at hospital discharge, 3 months, 6 months, and 12 months will be performed by readers blinded to treatment allocation. Arrhythmia occurrence (i.e., AF, nonsustained VT, VT or VF requiring device therapy) will be documented throughout the study period
- **Echocardiographic:** Change in left ventricular ejection fraction, chamber dimension, and tissue-strain pre-implant, at 6 months, and at 12 months to be performed by readers blinded to treatment allocation

Primary safety endpoint: Procedure-related complications will be assessed prospectively both acutely and throughout the study period, including:

- **Procedure related:** pneumothorax, perforation, pericardial effusion, or hemorrhage
- **System related:** implant site hematoma, implant site infection
- **Lead related:** lead dislodgement, lead fracture, inability to pace due to high threshold, phrenic capture

Randomization scheme: Patients will be allocated to HBP or standard CS lead at time of implant. Patients with LBBB and non-LBBB will be assigned to separate blocks and randomized separately.

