5. STUDY PROCEDURES

Pre-Implant

- Patients will be screened for study
- Pre-implant ECG reviewed (to be performed on day of screening)
- Baseline transthoracic echocardiogram (TTE) reviewed (does *not* need to be performed during inpatient hospitalization; outpatient or outside-hospital TTE report may also be performed)
- Patients who screen-in will be provided Kansas City Cardiomyopathy Questionnaire
- NYHA functional class to be determined by treating physician
- Operating physician will be informed of patient allocation to facilitate planning of procedure

Randomization, Implant, and Periprocedure Care

- RA and RV leads will be positioned per routine
 - o Arterial access for CS angiography or LV septal mapping may be performed at the discretion of the implanting physician in order to facilitate optimal lead placement

- 'LV' lead will be positioned in CS or at His-bundle based on allocation assignment
 - o The allocation assignment will be based on randomization schedule (developed using random number generator)
 - o The study coordinator will keep allocations in a sealed envelope and provide to implanting physician at time of procedure
 - o Patients with LBBB and non-LBBB will be randomized separately
 - o Each independent site will maintain their own randomization schedule
- If the initial allocated site is unsuccessful, alternative site will be pursued
- Intracardiac EGM information (surface QRS to LV site or QLV), pacing output, and lead position at final site will be recorded
- Predischarge ECG performed
- Predischarge device interrogation will be performed (as per standard of care)

2-Week Incision Check

- As per routine post-device care, all patients will be scheduled for routine postoperative device check at 2 weeks to evaluate incision
- Device interrogation (as per standard of care)

1-Month Visit

- Routine device interrogation
- Routine clinical check

(Note: Week 2 and Month 1 visits may be combined, per treating doctor discretion, for the simple post-op wound and clinical visit)

3-Month Visit

- Routine ECG
- Routine device interrogation
- Routine clinical check

6-Month Visit

- Post-implant TTE
- Routine ECG
- Routine device interrogation
- Routine clinical check
- Administration of Kansas City Cardiomyopathy Questionnaire
- NYHA functional class to be determined by treating physician

12-Month Visit

- Post-implant TTE
- Routine ECG
- Routine device interrogation
- Routine clinical check

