15. APPENDIXES

A. QUESTIONNAIRE

Kansas City Cardiomyopathy Questionnaire

B. SCHEDULE OF EVENTS (SCHEMA)

	Pre-Implant (Screening)	Implant & Periprocedure (Day 0)	Week 2 ^d	Month 1 ^d	Month 3	Month 6	Month 12	Year 2 & Year 3
Medical Records Review	X							X
Clinical Evaluation	X	X	X	X	X	X	X	
Electrocardiogram	X	X ^c			X	X	X	
Echocardiogram	X					X	X	
Urine Pregnancy Test ^a	X							
Kansas City Cardiomyopathy Questionnaire	X					X	X	
NYHA Functional Class Determination	X					X	X	
Randomization	X ^b							
Device Interrogation		X ^c	X	X	X	X	X	
Adverse Events		X	X	X	X	X	X	

^a Only for women of childbearing potential

^b Pre-procedure to facilitate planning of procedure

^c Pre-discharge

^d Week 2 and Month 1 visits may be combined, per treating doctor discretion

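### Randomisation is set both at implant and before the procedure, so the operator may know the arm before implant is certain, with no analysis group defined for patients never implanted

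*Combined protocol and SAP*

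**What the plan says.** Three statements put randomisation, or the release of the allocation, at the implant:

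- Section 2, study design: "Patients will be randomized, at the time of implant, to HBP versus CS pacing".
- Section 2, randomization scheme: "Patients will be allocated to HBP or standard CS lead at time of implant".
- Section 5, the list for randomisation, implant and periprocedural care: "The study coordinator will keep allocations in a sealed envelope and provide to implanting physician at time of procedure".

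Two put it earlier:

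- Section 5, last item of the Pre-Implant list: "Operating physician will be informed of patient allocation to facilitate planning of procedure".
- Appendix B, Schedule of Events: the only Randomization mark is in the Pre-Implant (Screening) column, with none on Day 0. Footnote b explains it as "Pre-procedure to facilitate planning of procedure".

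The same schedule column holds the baseline ECG, echocardiogram, KCCQ and NYHA class. In the Pre-Implant list, "Patients who screen-in will be provided Kansas City Cardiomyopathy Questionnaire" and "NYHA functional class to be determined by treating physician" come before the item about the operator. The list is not declared to be a sequence.

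Three further provisions bear on the point. Section 2 blinds the patients and the ECG and echo readers but not the treating physicians. Sections 3 and 5 have each site keep its own randomisation schedule. Section 6 studies patients by final treatment allocation and gives no rule for a patient who is randomised but not implanted.

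**The concern.** An envelope first handed over at the procedure cannot also inform planning before it. A site has to choose one instruction, and eight sites may choose differently within a trial of 40 patients.

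The choice matters because the interval between learning the arm and implanting the lead is when a patient can be deferred, withdrawn or judged unsuitable. If the operator already knows the arm, those decisions can depend on it. One of the exclusions in section 3, difficulty with follow-up, is a matter of judgement and is not defined further. Although section 3 is titled as covering withdrawal, it gives no withdrawal rule.

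Early randomisation is normally harmless if everyone is then analysed in the arm assigned. That protection is missing here, because a patient who is never implanted has no final treatment under section 6. Two results are exposed: the comparison of the arms, and Aim 1, the rate of successful His-bundle lead placement, which is measured at implant. If patients expected to be difficult leave the His-bundle arm before implant, the success rate rises without any change in the technique.

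**Working it through.** **1. Can the statements be reconciled?** Five places fix the timing. Three say at implant or at the procedure (section 2 twice, section 5 implant list). Two say before it (section 5 Pre-Implant list, Appendix B with footnote b). The kindest reading is that all mean shortly before the implant. The schedule allows that, since its only column before Day 0 is the screening one and a mark made that morning would have to go there. The envelope instruction does not: it releases the allocation at the procedure, which is too late for the planning named in the Pre-Implant list and footnote b. The conflict stands in the current text.

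**2. Does the early timing put allocation before the baseline measures?** Not demonstrably.

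- ECG: LBBB and non-LBBB patients are randomised separately, so QRS morphology must be known first.
- LVEF: every inclusion criterion needs it.
- NYHA class: the general eligibility list and criteria 1, 6, 7 and 8 name it. Criteria 2 to 5 do not.
- KCCQ: not needed for eligibility or stratification. It is completed by blinded patients.

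So ECG and LVEF must come first, NYHA class mostly must, and KCCQ need not. No text requires baseline KCCQ and NYHA class to be recorded before allocation is released.

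**3. The plan's sample size.** Inputs from section 6: d = 1, two-sided α = 0.05, power 0.80. For a two-sample t test the noncentrality is δ = d × √(n₁n₂/(n₁+n₂)), with n₁+n₂−2 degrees of freedom. Solving for equal arms gives n = 16.71, rounded up to 17 per arm, which reproduces the stated figure. At 17 v 17, δ = √(289/34) = 2.915 and power is 0.807. At 20 v 20, δ = √10 = 3.162 and power is 0.869. The margin is 40 − 34 = 6 patients, or 6/40 = 15%.

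**4. Size of pre-implant losses.** The documents give no rate, so the counts below are assumptions. Each loss is 1/40 = 2.5% of the sample.

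| Assumed losses | Arms | Power |
|---|---|---|
| 3, all from one arm | 17 v 20 | 0.838 |
| 6, split evenly | 17 v 17 | 0.807 |
| 8, split evenly | 16 v 16 | 0.781 |
| 10, split evenly | 15 v 15 | 0.753 |

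For 17 v 20, δ = √(340/37) = 3.031 with 35 degrees of freedom. Two or three losses use 2/6 to 3/6 of the margin, but power stays above 0.80. It falls below only when even losses from all causes together reach 8 or so.

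**5. Effect on Aim 1.** Let s be the number of His-lead successes among 20 patients assigned to His-bundle pacing. If three who would have failed leave before implant, the observed rate moves from s/20 to s/17, a relative rise of 20/17 − 1 = 18%. The three are again assumed, and s is at most 17. Selective loss of this size matters for the estimate even though it hardly matters for power.

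**The case against.** The strongest reply is that the wording needs tidying but the harm is thin, and much of that reply stands.

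A reader might infer that allocation is known before the baseline assessments, or at the same visit. The documents do not support either. Eligibility and stratification need the ECG, LVEF and, for most patients, NYHA class first. The operator is mentioned last in the Pre-Implant list. The schedule column is a stage rather than a single visit, since an outpatient or outside-hospital echocardiogram is accepted.

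A reader might also infer that physicians could pick a favourable baseline echocardiogram or bias the primary endpoints. LVEF is needed for eligibility, and QRS and LVEF changes are read blinded. NYHA class is not among the primary endpoints, and its follow-up grading is open to a physician who knows the arm whenever randomisation takes place.

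Nor can a threat to power be inferred: three losses from one arm still leave the required 17 in that arm.

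Finally, section 6 is silent on patients never implanted. It does not say they are excluded, and analysis by final treatment is a separate weakness that a later randomisation would not cure.

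The reply leaves three things untouched: the contradictory instructions, an unblinded operator who under one of them knows the arm while implant can still be deferred or abandoned, and the absence of any rule that keeps such a patient in the assigned arm.

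**Conclusion.** The concern holds as a contradiction over when randomisation takes place and the allocation is released, with a route to selection bias under the earlier timing. The harm is possible, not shown. It requires that some patients are randomised and then not implanted, and that this happens more often, or for different patients, in one arm. The documents give no rate for it. The required sample size is unaffected, and the effect on power is small (0.838 at 17 v 20). The possible effect on Aim 1 is larger in relative terms: 18% if three patients who would have failed leave the His-bundle arm. The order of baseline assessments and allocation is a gap in the text, not evidence that allocation comes first. The change is worth making because it is cheap and removes a source of bias in a small trial with eight separately kept randomisation schedules.

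**What to change.** State one time point, in the same words, in both places in section 2, in both lists in section 5, and in the Schedule of Events with its footnote b.

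- Move the Randomization mark to Day 0.
- Open the envelope on the day of the procedure, only after consent, ECG, echocardiogram, KCCQ and NYHA class are recorded and implant is confirmed. The operator can still be told that day, before starting.
- Log the time of opening on the case report form.
- Add to section 6 that every randomised patient is accounted for in the arm assigned, including any not implanted, with the reason. State the denominator for Aim 1 accordingly.

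The cost is rewording in those places, one time field on the form and less planning notice for the operator. The sample size does not change. The wider choice to analyse by final treatment allocation needs its own decision; this change does not settle it.

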More recently, the feasibility of resynchronizing ventricular activation by permanent pacing of the His bundle region has been described, with clear clinical advantages over traditional RV apical pacing.¹⁹⁻²³ This technique is an FDA approved therapy for pacing. The physiologic benefit of permanent His bundle pacing (HBP) is the ability to stimulate the ventricles through the intrinsic His-purkinje system, which results in synchronous electrical and mechanical activation. Furthermore, similar to CRT, reports of hyper-response—typically described as patient functional recovery to an LVEF $\geq 50\%$, has been reported with HBP after restoration of normal intrinsic conduction.²⁴⁻²⁶ Perhaps even more provocatively, in a recent study in which patients were implanted with four leads (RA, RV, CS LV lead, and HBP lead), both modes of resynchronization (HBP and CS) were studied utilizing a cross-over design, and both were found to be associated with similar benefit (with patients acting as their own controls).²⁷ Indeed, HBP may have theoretical advantages over CRT using a coronary sinus lead, which is associated with limited coronary venous anatomy and complications that include coronary sinus dissection, venous perforation, and the potential for proarrhythmia. While both techniques comprise the standard-of-care for pacing, direct comparison of HBP with traditional

CS lead position for CRT has not yet been investigated, and is the motivation behind the His-SYNC Study.

B. OBJECTIVES

We hypothesize that:

- a. In patients with advanced heart failure and evidence of intraventricular conduction delay who meet criteria for CRT, HBP may be safely achieved *and*
- b. HBP is associated with similar echocardiographic and clinical outcome as conventional CS pacing during CRT

Specific aims:

Aim 1: To determine the overall rate of successful His-bundle lead placement at the time of implant of CRT. Patients randomized to HBP but who cannot be successfully implanted with a HBP lead will cross-over to traditional CS lead position.

Aim 2: To assess the impact of HBP versus CS pacing on acute and mid-term outcomes.

Acute outcomes include incidence of periprocedural complication and change in QRS duration pre-and post-pacing. Mid-term outcomes include echocardiographic response at 6 and 12 months along with a composite clinical outcome of heart failure hospitalization, arrhythmia, and all-cause mortality.

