6. STATISTICAL PLAN AND CONSIDERATIONS

Sample size estimation:

The sample size for this study is a total of 40 subjects (20 HBP and 20 CS lead). The sample size estimate was based on a goal to observe an absolute 10% difference in LVEF between the two groups, leading to a Cohen's d statistic of 1. With a significance level (α) = 0.05 and a power of 0.8, at least 17 subjects will be required in each group. A goal of 40 subjects was made to allow for possible dropout during the study period.

Statistical methods:

Patients will be studied based on the final treatment allocation. Crossovers and reasons for crossover will also be recorded. Fisher's exact or the Chi-Square test will be used for categorical variables, and continuous parameters will be compared by the two-tailed unpaired Student's t test and the F test for analysis of variance (ANOVA), as needed. Kaplan-Meier method will be used for computing the event free survival curves. Each implant strategy will be compared within this cohort of patients for its impact on percent change QRS duration, LVEF, and as clinical outcome. Multiple logistic regression and multiple regressions using the Cox proportional hazards model will be performed to determine the independent association of each of the implant variables with LVEF and clinical outcome.

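### Only HBP patients may switch site for insufficient QRS narrowing, although QRS change is a primary endpoint, and the paced QRS at the abandoned site is not listed for recording

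*Combined protocol and SAP*

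**What the plan says.** Section 2 (Study Design) gives different exits to the two arms. An HBP patient may cross over if the lead lacks stability or acceptable output, "or if QRS width does not narrow by at least 20% or to a QRS width of" 130 msec or less. A CS patient may cross over if the "CS lead cannot be placed due to difficult cannulation of the CS, limited branches at the posterolateral or lateral wall, or phrenic nerve capture". No section sets a QRS target for a CS lead.

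Section 2 lists among the primary endpoints "Change in QRS duration between pre-implant and at hospital discharge, 3 months, 6 months, and 12 months". Aim 2 in Section 1 adds: "Acute outcomes include incidence of periprocedural complication and change in QRS duration pre-and post-pacing". Section 6 plans the comparison: "Each implant strategy will be compared within this cohort of patients for its impact on percent change QRS duration, LVEF, and as clinical outcome".

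On recording, Section 5 says "Intracardiac EGM information (surface QRS to LV site or QLV), pacing output, and lead position at final site will be recorded". The next ECG it schedules is the pre-discharge one, after any switch. Section 6 says: "Patients will be studied based on the final treatment allocation. Crossovers and reasons for crossover will also be recorded". That captures why a patient crossed over, but not the QRS value that triggered it. No section lists the paced QRS at an abandoned site.

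**The concern.** The variable that triggers the switch is also an endpoint. An HBP patient whose QRS narrows poorly is given a second site before the discharge ECG. A CS patient whose QRS narrows just as poorly keeps the first site. Blinded ECG reading does not help, because the selection happens before the tracing is taken.

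At stake is what the QRS result means. The hypotheses and Aim 2 speak of HBP versus CS pacing, but from discharge onward the QRS data compare HBP plus a QRS-triggered rescue with CS alone. A comparison of the sites themselves needs the paced QRS at the allocated site. The implanter must measure it in HBP patients to apply the rule, but the plan does not send it to the database. Eight sites that function independently cannot be expected to keep it uniformly without an instruction.

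**Working it through.** **The plan's own figure.** The only sample-size calculation is for LVEF (Section 6): d = 1, two-sided alpha 0.05, power 0.8, at least 17 per group. It reproduces: exact t-test power is 0.781 at 16 per group and 0.807 at 17. There is no corresponding figure for QRS, so the size of this problem has to be illustrated.

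**Inputs.** From the documents: the 20% and 130 msec thresholds, 20 patients per arm, and the unpaired two-tailed t test. Assumed: the sites are equally good; percent narrowing H at the His site and C at the CS site are each normal with mean m = 20 and SD 10; the within-patient correlation r between sites is 0.5; baseline QRS has mean 165 msec and SD 20, cut at 120; an HBP patient who meets neither threshold crosses over; and there are no placement failures.

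**Step 1: who crosses.** Simulation gives a crossing fraction p = 0.39, about 8 of 20. The crossers' mean narrowing at the His site is about 11.1%, which is 8.9 points below m. Because the sites are correlated, their expected narrowing at the CS site is 20 − 0.5 × 8.9 = 15.55%.

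**Step 2: gap by randomised arm.** Only the crossers' values change, so

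gap = p × [E(C | crossed) − E(H | crossed)] = 0.39 × (15.55 − 11.1) = 1.74 points in favour of HBP.

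Equivalently, gap = p × (1 − r) × 8.9:

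- r = 0.9: 0.39 × 0.1 × 8.9 = 0.35
- r = 0: 0.39 × 1 × 8.9 = 3.5
- r = 1: 0
- r = 0.5 with half of eligible patients crossing (p = 0.195): 0.195 × 4.45 = 0.87

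**Step 3: gap by final treatment.**

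- HBP patients who stay: (20 − 0.39 × 11.1) / 0.61 = 25.69
- CS patients plus crossers: (20 + 0.39 × 15.55) / 1.39 = 18.75
- gap = 6.94 points; at half take-up, 2.88 points

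**Step 4: false-positive rates, 20 per arm, nominal 5%.**

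| Analysis (r = 0.5) | All eligible cross | Half cross |
|---|---|---|
| Final treatment | 56% | 14% |
| Randomised arm | 8.8% | 6.0% |
| First-site QRS, randomised arm | 5.0% | not affected by crossing |

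**Step 5: sensitivity.** With baseline mean 150 msec, 28% cross and the gaps are 1.40 points (randomised arm) and 4.98 points (final treatment). Over 48 scenarios (mean 10–25%, SD 10–15, correlation 0–0.9, take-up 50–100%) the randomised-arm gap runs from 0.15 to 5.54 points and the final-treatment gap from 1.57 to 17.75. If the rule is read as requiring both thresholds to be met, a run with baseline SD 18 and otherwise central inputs gives 62.5% crossing, 1.8 points by randomised arm and 10.4 by final treatment.

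**The case against.** The strongest reply is that this is a deliberate comparison of strategies. Section 6 speaks of implant strategies, Aim 1 measures HBP success with cross-over on failure, and a QRS threshold is a sensible working definition of success. That stands, and it is why the bail-out should stay. But the plan never says that its QRS results are to be read this way.

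A second reply is that the effect is small once patients are analysed as randomised. This largely stands. Over the 48 scenarios the median gap is 1.4 points and the median false-positive rate 6.9%; the rate exceeds 10% in only 8, all with zero correlation. The correlation drives the answer and the documents do not give it. Section 1 notes that a patient's substrate may limit response, so some agreement between sites is plausible.

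A third reply is that Section 5 applies to both arms: "If the initial allocated site is unsuccessful, alternative site will be pursued". It does not define failure, however, and the only stated grounds are those in Section 2. A CS lead that is placed and paces has not failed on any of them.

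Several stronger readings are tempting but not supported:

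- That the rule alone produces a 56% false-positive rate. That figure also needs final-treatment grouping.
- That bias is inevitable unless each patient responds identically at both sites. The formula in the working shows that it is enough for the crossers' mean to be the same at both sites.
- That the first-site value will certainly be lost. It is not listed for recording, but nothing shows that sites would discard it.
- That first-site QRS removes the bias completely. Section 2 expects placement failures in both arms, and some of those patients will have no usable value.
- That LVEF, clinical or safety results are shown to be biased. This point concerns QRS only.

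**Conclusion.** The point holds as a matter of text: the QRS exit is open to one arm only, QRS change is a listed primary endpoint and an Aim 2 outcome, and the paced QRS at the abandoned site is not listed for recording. The comparison will tend to favour HBP when the sites are equally good.

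The size attributable to the rule itself is the randomised-arm figure: about 1.7 points of narrowing in the central case, about 0.35 to 3.5 as the correlation falls from 0.9 to 0, and about 0.9 at half take-up. The rise to about 7 points under the planned grouping belongs mainly to the separate question of analysing by final treatment. All these sizes rest on assumed inputs. Severity is minor to moderate: a cheap improvement to one of several co-listed endpoints, not a flaw in the LVEF sample size or in the rationale for the bail-out.

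**What to change.** Keep the HBP bail-out. Then:

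1. In Section 5, require that the paced 12-lead QRS tracing at the initially allocated site be recorded and stored before any cross-over, in both arms, and read by the existing blinded ECG readers.
2. In Section 6, make percent change from pre-implant to this first-site value, by randomised arm, the acute comparison of the sites. Report how many patients in each arm have no first-site value because of placement failure, and give a sensitivity analysis for them.
3. State that discharge, 3-, 6- and 12-month QRS results compare strategies: HBP with a QRS-triggered switch versus CS without one.

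Extending the QRS criterion to CS patients is not part of this recommendation. It would restore symmetry but add CS-to-HBP cross-overs, so it is a trade-off.

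The cost is one stored tracing per patient, its blinded reading, and a few sentences. The HBP measurement is already needed to apply the rule; the CS arm needs one extra reading at implant. Some first-site values will be missing, so the bias is reduced but not guaranteed to be zero.

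### Several clinical, QRS and echocardiographic measures are all listed as primary with no ranking or multiplicity rule, and the LVEF difference that sized the trial has no visit

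*Combined protocol and SAP*

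**What the plan says.** Section 2 (Study Design) has one plural heading for primary endpoints, introduced by "A combination of clinical, electrocardiographic, and echocardiographic endpoints will be prospectively studied". Three bullets follow:

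- Clinical: a "composite of heart failure hospitalization, VT/VF, and any-cause mortality at 12 months". This bullet is individually labelled the primary clinical endpoint.
- Electrocardiographic: "Change in QRS duration between pre-implant and at hospital discharge, 3 months, 6 months, and 12 months", plus arrhythmia occurrence over the study period.
- Echocardiographic: "Change in left ventricular ejection fraction, chamber dimension, and tissue-strain pre-implant, at 6 months, and at 12 months".

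A separate primary safety endpoint comes after these.

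Section 6 (Statistical Plan and Considerations) bases the sample size on "a goal to observe an absolute 10% difference in LVEF between the two groups", with Cohen's d of 1, alpha 0.05, power 0.8 and at least 17 per group, raised to 40 in total for dropout. It gives no visit and does not say whether LVEF means change from pre-implant or the follow-up value. The methods paragraph compares the two strategies "for its impact on percent change QRS duration, LVEF, and as clinical outcome", with no order, visit or division of alpha. The statistical summary at the front of the protocol adds none.

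Section 1.B does not settle the visit. Aim 2 reads "Mid-term outcomes include echocardiographic response at 6 and 12 months" and prefers neither. Hypothesis (b) is that "HBP is associated with similar echocardiographic and clinical outcome as conventional CS pacing during CRT".

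**The concern.** The sample size points to LVEF and the individual label points to the clinical composite. No section says which one decides the trial. Even if LVEF is taken as the deciding measure, 6 and 12 months remain equally open. Followed as written, the plan lets both choices be made after the data are seen, so a chance difference on one of several listed measures could be reported as a primary result at a nominal 5%.

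There is a risk in the other direction too. Hypothesis (b) predicts similar outcomes, while the sample size is built to detect a difference. With no statement of what a null result means, a non-significant LVEF comparison could be taken as confirming similarity.

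**Working it through.** **1. The plan's own figure.** Inputs from section 6: difference 10 points, d = 1 (so the implied SD is 10/1 = 10 points; the SD itself is not stated), two-tailed unpaired t test, alpha 0.05, power 0.8. Power comes from the noncentral t with 2n - 2 degrees of freedom and noncentrality d × sqrt(n/2).

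| n per group | Noncentrality | Power |
|---|---|---|
| 16 | 2.83 | 0.781 |
| 17 | 2.92 | 0.807 |
| 20 | 3.16 | 0.869 |

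So 17 per group is reproduced for one LVEF test at one visit. The room for dropout is 20 - 17 = 3 per group, or 3/20 = 15%.

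**2. How many comparisons.** Section 6 names three outcomes: QRS, LVEF and clinical outcome. Section 2, counted by measure and time, gives 1 clinical + 4 QRS + 3 × 2 echocardiographic = 11, or 12 with arrhythmia occurrence. LVEF alone has two visits.

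**3. Chance of at least one false difference.** This assumes that each comparison is tested at two-sided 0.05 and that any one significant result can be claimed as primary. For k independent tests it is 1 - 0.95^k. For correlated tests I used equally correlated normal statistics, integrated numerically. The documents give no correlations, so a range is shown.

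| Comparisons | Independent | Correlation 0.5 | Correlation 0.9 |
|---|---|---|---|
| 2 LVEF visits | 1 - 0.95² = 0.098 | 0.091 | 0.070 |
| 3 outcomes in section 6 | 1 - 0.95³ = 0.143 | 0.125 | 0.084 |
| 11 measure-by-time comparisons | 1 - 0.95¹¹ = 0.431 | 0.304 | 0.131 |

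The independent entry for 11 comparisons is shown only for completeness; it is not realistic for repeated measures in the same patients. There is no inflation above 5% if LVEF at one fixed visit is the sole primary, or if all endpoints must be significant together.

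**4. What a non-significant LVEF result could exclude.** With SD 10, the half-width of the 95% CI is t(0.975, 2n - 2) × 10 × sqrt(2/n):

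- n = 17: 2.037 × 10 × sqrt(2/17) = 6.99 points.
- n = 20: 2.024 × 10 × sqrt(2/20) = 6.40 points.

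At a true difference of 5 points (d = 0.5, chosen for illustration), power is 0.293 at 17 and 0.338 at 20 per group. The result would be non-significant with probability 1 - 0.293 = 0.707 or 1 - 0.338 = 0.662.

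**5. How far the 17 per group carries over.** Two assumed departures show its limits:

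- If the SD of the chosen LVEF quantity is 12, power is 0.65 at 17 and 0.73 at 20 per group. If it is 8, power is 0.94 and 0.97.
- Section 6 analyses patients by final treatment allocation, and section 2 permits crossover, so the analysed groups may be unequal. With 34 evaluable patients, a 22/12 split gives power 0.77 and a 24/10 split gives 0.73.

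**The case against.** The clinical composite is the only item individually called a primary endpoint, and it is fixed at 12 months, so it might be argued that the plan does name a primary. It names one within the clinical domain. The composite is one of three bullets under a plural heading, is not placed above the others and did not size the trial. The opposite argument, that sizing on LVEF makes LVEF the primary, is suggestive, but no section says so and the visit would still be open.

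The error rates are conditional, and that objection stands. The plan nowhere says that any one significant result suffices. A reader might go further and infer a 43% false-positive rate. That needs all 11 comparisons to be tested and to be independent, yet they include the same measures repeated in the same patients, and section 6 lists only three outcomes. Testing all 11 would give a higher rate than testing three, but 43% should not be cited as the size of the problem.

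It is also fair to say that hypothesis (b) concerns similarity, so the likelier misreading is no difference, therefore similar. Multiple endpoints do not create that problem, and naming one primary does not give hypothesis (b) a margin or a test. It does need a sentence in the plan.

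Finally, nothing in the documents prefers 12 months to 6 for LVEF. Choosing 12 is a judgement.

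**Conclusion.** The concern holds: the protocol leaves both the deciding endpoint and the LVEF visit undefined, and the plan as written does not secure the stated 5% error rate. On the assumption that any one result at two-sided 0.05 can be claimed as primary, the false-positive chance is about 7-10% across two LVEF visits and 8-14% across the three section 6 outcomes, for correlations from 0.9 down to independence.

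A reader might infer that the sample size is therefore wrong. It is not. Seventeen per group is right for a single LVEF test, provided the implied SD of 10 applies to the LVEF quantity analysed and the compared groups are about equal. Separately, a 95% CI half-width of about 6.4-7.0 points is too wide for a null result to be read as similarity by itself.

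This should be corrected. It leaves the decisive result undefined but does not invalidate the planned number of patients.

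**What to change.** Before any between-group efficacy comparison is looked at, amend sections 2 and 6 as follows:

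1. Name LVEF, the measure that sized the trial, at one visit as the single primary efficacy endpoint, at two-sided alpha 0.05. Twelve months is a reasonable option because it matches the composite and the study duration. Its cost is more exposure to death and dropout than at 6 months; power at d = 1 falls to 0.78 once a group size of 16 is reached.
2. State whether the endpoint is change from pre-implant or the follow-up value, and which analysis groups are compared, given that crossover is permitted.
3. Make the other LVEF visit and the remaining efficacy endpoints secondary, reported with 95% CIs and no confirmatory claim. This includes the clinical composite despite its current label. Leave the separate primary safety endpoint in place.
4. Add that a non-significant LVEF difference does not establish the similarity in hypothesis (b), and that the difference will be reported with its 95% CI.

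The cost is a protocol amendment at eight sites, one of which relies on the coordinating site's IRB, and loss of primary status for the other efficacy endpoints. Data collection does not change, and N = 40 stands under the two conditions given in the verdict. Splitting alpha equally (Bonferroni) is the alternative. At d = 1 it would lower LVEF power from 0.81 at 17 per group (0.87 at 20) to 0.71 (0.79) for two visits or 0.65 (0.74) for three outcomes.
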